10.1.2 Analysis of mean trough total IgG data

Mean trough total IgG concentration for the IGSC 20% treatment phase will be calculated as the average of all steady state trough concentrations measured during the IGSC 20% Treatment Stage 2, ie, total IgG trough levels measured at the following visits: SC#17, #18, #20, #24, #28, #32, #36, #40, #44, #48, #52, and #53. Comparison will be made to the mean trough total IgG concentration for the previous IgG regimen (either IVIG or other SCIG products) obtained during the Screening/Previous Regimen Phase. For subjects entering study on a previous IVIG regimen, the mean trough for the previous IgG regimen will be calculated as the average of the 2 trough concentrations at pIV#1 and pIV#2. For subjects entering study on a previous SCIG regimen, the mean trough for the previous IgG regimen will be calculated as the average of the 2 trough concentrations at pSC#1 and Baseline/SC#1.

Mean trough data will be summarized by study phase. Mean trough summary and analysis will be based on the IgG population. The summaries will be provided by adult vs. pediatric subjects and overall.

10.1.3 Analysis of serial total IgG data

The analyses of serial total IgG concentrations will be based on the PK population.

Serial total IgG concentrations prior to and after SC#17 infusion in adult subjects in the PK subset will be presented in a listing by subject, study phase, visit, date, and scheduled/nominal sampling time point. The data listing will provide details of all planned total IgG collection time points relative to the start of SC#17 infusion (scheduled and nominal times as shown in Section 4.1.1.1), actual collection date and clock times and actual elapsed times from the start of the infusion, as well as total IgG concentrations. If any concentration values are excluded from the PK analyses, they will be flagged in the listing.

The clock time for the start and completion of the infusion, the actual duration (time interval) for the infusion, and the actual volume infused will be presented in a separate listing.

Serial total IgG concentrations will be summarized by the scheduled/nominal time point. The summaries will include n, mean, SD, coefficient of variation (%CV), median, minimum, maximum, and geometric mean.

Total IgG concentration vs. time curves for individual subjects will be presented with the actual elapsed time from the start of the SC#17 infusion plotted on the x-axis. Individual concentration vs. time plots will also be presented for all subjects on the same figure (spaghetti plot). For all subjects combined, mean or median total IgG concentration vs. time curves will be presented in one figure with the nominal time (see Section 4.1.1.1) plotted on the x-axis. All total IgG concentration vs. time curves will be plotted on both the linear and the semi-log scale.

10.2 Calculation of PK parameters

The PK parameters of serial total IgG following the IGSC 20% infusion at SC#17 in adult subjects in the PK subset will be determined as appropriate and as data permits. The PK parameters include $AUC_{0-7days}$, C_{max} , and t_{max} .

Pharmacokinetic parameters will be calculated by Nuventra Pharma Sciences using Phoenix® WinNonlin® software, version 6.3 or later (Certara USA, Inc. [Princeton, NJ]).

The PK parameters of interest are determined as follows:

$AUC_{0-7days}$	area under the concentration vs. time curve from time 0 to 7 days, calculated by a combination of linear and logarithmic trapezoidal methods and expressed in the unit of concentration \times time (eg, mg \times hour/dL). The linear trapezoidal method will be used for all incremental trapezoids arising from increasing concentrations and the logarithmic trapezoidal method will be used for those arising from decreasing concentrations.
C_{max}	the observed maximum total IgG concentration following drug infusion obtained directly from the experimental data without interpolation, expressed in concentration units (eg, mg/dL).

t_{\max} the observed time to reach maximum total IgG concentration obtained directly from the experimental data without interpolation, expressed in time units (hour). If there are more than one maximum observed concentration, the t_{\max} is the time to the first observed maximum concentration.

10.3 Descriptive Statistics of PK Parameters

Descriptive statistics including n, mean, SD, %CV, median, minimum, and maximum will be calculated for all PK parameters. Geometric mean and 90% CI for the geometric mean will also be calculated for all PK parameters (except t_{\max}). The analyses of PK parameters will be based on the PK population.

11 SAFETY ANALYSIS

Safety analyses will be based on the Safety population.

11.1 Adverse Events

All reported AEs will be coded and summarized by system organ class (SOC) and preferred term (PT) according to MedDRA.

AE causality will be classified and assessed by the investigator. If the causality is “definitive”, “probable”, “possible”, or “doubtful/unlikely”, the event will be defined as a suspected adverse drug reaction (ADR). A suspected ADR with a causal relationship of “definite” will be defined as an adverse reaction (AR); thus, ARs are a subset of suspected ADRs. If the causal relationship is labeled as “unrelated”, then it will be considered that the AE is not imputable to the study treatment and it is not a suspected ADR.

For summary purposes, AEs will be classified as treatment emergent AEs (TEAEs) or non-treatment emergent AEs (non-TEAEs) depending on the comparison of AE onset date/time with the start of study treatment (ie, start of the infusion at Baseline/SC#1). A TEAE will be defined as an AE which occurred on or after the start of study treatment. For adverse events with incomplete start dates, the same algorithm for missing or partial date information described in Section 8.1 (Prior and Concomitant Medication) will be used for determination of treatment emergent or not. Non-TEAEs will be summarized separately from TEAEs. TEAEs will be further characterized within each study phase based on the onset date/time relative to the first infusion date/time in each study phase.

The incidence of AEs, suspected ADRs, ARs, non-serious AEs, SAEs, and AEs by severity and causal-relationship to the investigational product will be summarized by study phase using descriptive statistics. At each level of summation, a subject will only be counted once per system organ class or preferred term using the most severe or highest causal relationship AE. All infections and local injection site reactions that meet the definition of an AE (see Section 4.3.1 of the protocol for details) will be summarized with other AEs.

Summaries will also be provided for the total number of events, the rate per infusion, and the rate per exposure week. The rate per infusion will be calculated as:

$$\text{Total number of events} / \text{Total number of infusions received}$$

The rate per exposure week will be calculated as:

$$\text{Total number of events} / \text{Total duration of exposure in weeks}$$

Subjects with deaths, SAEs, and AEs leading to premature discontinuation from the study will be listed.

Temporally-associated AEs defined as those occurring during or within 72 hours following the end of investigational product infusion will be separately summarized. For AEs that occur during study drug infusion, the infusion rate in effect at the time of onset of the AE, the time when the AE is first reported and the time when the AE changes materially in intensity and/or resolves will be listed.

Local infusion site reactions during the IGSC 20% treatment phase that do not meet the definition of an AE will be separately summarized by IGSC 20% infusion week and overall. The summaries will be presented by preferred term and infusion site, and include the number and percentage of subjects with any event, the total number of events, and the rate per infusion. The percentage of subjects with any local infusion site reactions and the rate per infusion will also be plotted vs. IGSC 20% infusion week number.

All AEs including infections and local infusion site reactions that meet the definition of an AE will be presented in a data listing. Local infusion site reactions that do not meet the definition of an AE will be listed separately.

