4.3 Adverse Event Definitions

4.3.1 Adverse Events

An AE is defined as any untoward medical occurrence in a subject or clinical investigation subject administered a medicinal product or study treatment and which does not necessarily have a causal relationship with this administration. An AE can therefore be any unfavorable and unintended sign (including any abnormal laboratory finding, for example), symptom, or disease temporally associated with the use of a medicinal product, whether or not considered related to the medicinal product.

Any AE that occurs at any time between the signing of the ICF and the last day of the subject's participation in the clinical trial must be reported and recorded in the AE eCRF.

All local infusion site reactions will be recorded in the eCRF. The subset of local infusion site reactions where the symptoms/signs lead to infusion interruption or discontinuation, require concomitant medication, or have an impact on the general condition of the subject as judged by the Investigator will be considered as AEs.

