For any subject, all AEs that occur at any time from the beginning of IP administration until the final visit of the clinical trial will be considered as treatment emergent AEs (TEAEs).

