4.3.7 Adverse Event Documentation

All AEs and SAEs occurring after the subject has **signed the ICF through the Final Visit (i.e., end of study)** must be fully recorded in the subject’s eCRF or SAE form and medical record. If no AE has occurred during the study period, this should also be indicated in the eCRF.

It is the responsibility of the Investigator to ensure that AEs are appropriately recorded.

At each visit, AEs will be elicited by asking the individual a non-leading question such as “Do you feel different in any way since the last visit?” Moreover, AEs will also be collected through directly observed events or spontaneously volunteered by the subject. Clearly related signs, symptoms and abnormal diagnostic procedures should preferably be grouped together and recorded as a single diagnosis or syndrome wherever possible.

The following variables must be recorded in the AE eCRF:

1. The verbatim term (a diagnosis is preferred)
2. Date/time of onset
3. Date/time of resolution
4. Severity (mild, moderate, severe)
5. Causality (unrelated, doubtful/unlikely, possible, probable, definite)*
6. Seriousness (yes, no)
7. Action taken (with regard to IP)
8. Other action (to treat the event)
9. Outcome and sequel (follow-up on AE)

**Causality assessment will be made only when the AE occurs after the subject has initiated at least one infusion of the IP. An AE occurring before subject's exposure to IP will be always labeled as "unrelated".*

For AEs that occur during infusions, the infusion rate in effect at the time of onset of the AE, the time of onset of the AE and the time of AE change materially in intensity and/or resolve will be captured in the eCRF.

In addition to the Investigator's own description of the AEs, each AE will be encoded according to the Medical Dictionary for Regulatory Activities (MedDRA).

For example, a laboratory test abnormality considered clinically relevant, e.g., causing the subject to withdraw from the study, requiring treatment or causing apparent clinical manifestations, or judged relevant by the Investigator, should be reported as an AE. Each event must be described in detail along with start and stop dates, severity, relationship to IP, action taken and outcome. Each event must be adequately supported by documentation as it appears in the subject's medical or case file.

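### Treatment-emergent status depends on onset date alone, so an AE that begins on the previous IgG product and worsens on IGSC 20% is tabulated as non-treatment-emergent and not as a suspected ADR

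*SAP*

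**What the plan says.** **TEAE rule.** SAP section 11.1 separates TEAEs from non-TEAEs "depending on the comparison of AE onset date/time with the start of study treatment", that start being the Baseline/SC#1 infusion. It then defines the term: "A TEAE will be defined as an AE which occurred on or after the start of study treatment". Assignment to a study phase also follows onset: "TEAEs will be further characterized within each study phase based on the onset date/time relative to the first infusion date/time". Protocol section 4.3.3 treats as treatment-emergent "all AEs that occur at any time from the beginning of IP administration until the final visit of the clinical trial". Neither text mentions an increase in severity or a change to serious.

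**Collection period.** Protocol section 4.3.1 requires reporting of "Any AE that occurs at any time between the signing of the ICF and the last day" of participation. Section 3.6.1 allows up to 8 weeks for the Screening/Previous Regimen Phase, and section 3.6.2.1 has sites record AEs in that phase, including infusion reactions.

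**Causality.** The footnote in protocol section 4.3.7 reads: "Causality assessment will be made only when the AE occurs after the subject has initiated at least one infusion of the IP". It adds that an AE arising before the subject's "exposure to IP will be always labeled as" unrelated. Under protocol section 4.3.3 and SAP section 11.1, an unrelated AE is not a suspected ADR. Section 4.3.3 also says that the unrelated label is unavailable when the investigator or sponsor cannot exclude a causal link.

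**The concern.** A treatment-emergent definition should capture what happens to the subject on the product. That includes a condition already present at the first dose that then becomes more severe or serious. An onset-only rule captures the first appearance of an AE and ignores its later course.

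The gap is a practical one here. Every subject enters on another IgG product, and AEs on that product are recorded. Subjects coming from IVIG start IGSC 20% about 7 days after their last IVIG infusion (protocol section 3.3.2; 6 to 9 days under section 3.6.2), so an AE that followed that infusion can still be open at SC#1. Non-serious infections are also recorded as AEs, and the protocol does not make them a screen failure in themselves.

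What is at stake is the TEAE and suspected-ADR tables. There is no control arm in which the same rule would remove similar events, and the omission can only lower the counts attributed to IGSC 20%.

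**Working it through.** The plan gives no figure to reproduce. The check traces one case through the written rules: an AE with known onset in the Previous Regimen Phase, still ongoing at SC#1, and worse afterwards.

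1. **TEAE flag (SAP 11.1).** Onset precedes the start of SC#1, so the AE is a non-TEAE. The protocol 4.3.3 definition turns on when an AE occurs and has no worsening clause that would change this.
2. **Study phase (SAP 11.1).** TEAEs are placed in a phase by onset, so the worsening does not appear as a Treatment Stage 1 or Stage 2 TEAE.
3. **Causality (protocol 4.3.7).** The AE arose before any IGSC 20% infusion, so no causality assessment is made and it is labelled unrelated.
4. **Suspected ADR (protocol 4.3.3, SAP 11.1).** Unrelated means that it is not a suspected ADR, and so not an AR.
5. **Effect of the worsening.** None of steps 1 to 4 refers to what happens after onset, so the worsening changes no result.

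**Could another rule rescue the case?**

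- *A new record at worsening.* This would give a new onset date and correct steps 1 to 4. Neither document instructs it.
- *Capture of intensity changes.* Protocol 4.3.7 asks for the time of a material change only for AEs that occur during infusions. SAP 11.1 sends this to a listing, not to the TEAE flag.
- *Partial dates.* SAP 11.1 borrows the section 8.1 rule, which imputes missing parts as late as possible and so leans towards TEAE status. It does nothing when the onset date is known.

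**The two causality rules side by side.** Protocol 4.3.7 fixes the label by timing. Protocol 4.3.3 withholds the same label when a causal role cannot be excluded. For an AE that worsens after SC#1 and for which the product might be responsible, both cannot be followed.

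**Number affected.** The documents give no AE counts. Purely as an illustration, assume 0.1 to 0.3 AEs per subject ongoing at SC#1, of which 10% to 20% worsen. With the 60 subjects planned:

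- low: 60 × 0.1 × 0.10 = 0.6 events
- high: 60 × 0.3 × 0.20 = 3.6 events

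Neither input comes from the documents, so this range is not an estimate.

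**The case against.** The strongest reply is that little is hidden. Non-TEAEs have their own summary and all AEs are listed. Deaths, SAEs and AEs leading to discontinuation are listed without a TEAE restriction (SAP 11.1), and protocol 5.1.5 adds narratives. The sponsor makes its own causality assessment for SAEs (protocol 4.3.3), and SAEs are reported within 24 hours whatever their attribution (4.4.1). Laboratory worsening shows in changes from baseline and shift tables (SAP 11.2). All of this stands. A reader might infer that worsening disappears from the safety report, and the documents do not support that. But these safeguards do not restore the TEAE or suspected-ADR counts, and a non-serious worsening gets no second look at causality.

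The pool is also limited. Eight weeks is the IVIG maximum; the SCIG phase is 4 weeks (protocol 3.3.2), and 10 days is the anticipated minimum (3.1). A reaction to the last IVIG dose must persist for about a week and then worsen. An SBI or a hospitalization for infection in this phase is a screen failure, and eligibility is re-assessed at Baseline. Against at most 60 × 52 = 3,120 planned infusions, a few events are unlikely to alter the safety conclusion. This supports calling the effect small. It does not support leaving the rule as it is.

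Other rules lean against the product: partial onset dates are imputed late, and doubtful/unlikely events count as suspected ADRs. Those rules act on other events and do not offset this one.

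Two further inferences are tempting and unsupported. One is that the non-TEAE table will show the severity reached on IGSC 20%. Protocol 4.3.7 asks for a severity without saying whether it is the initial, current or worst grade, and it does not bar a second record. The other is that the most severe events are affected most. Nothing in the documents bears on that.

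**Conclusion.** The point holds as a defect in the rule. As written, an AE with onset before SC#1 that worsens on IGSC 20% is a non-TEAE, is labelled unrelated and is not a suspected ADR. The conclusion assumes that sites do not open a new record at worsening. An eCRF completion guideline might tell them to, but neither document does.

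The error is in the product's favour, and there is no control arm. Its size cannot be derived from the documents and is probably small. The primary SBI analysis does not use the TEAE flag and is unaffected.

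The conflict between protocol sections 4.3.3 and 4.3.7 needs resolving whatever the number of events. One reservation concerns versions: the SAP names protocol Version 3.0 as its basis, while the protocol supplied carries the Version 2.0 change summary. The automatic unrelated label is therefore confirmed only for the supplied text.

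**What to change.** 1. **SAP 11.1.** Define a TEAE as an AE with onset on or after the start of the SC#1 infusion, or with earlier onset that increases in severity or becomes serious on or after that time. Align the sentence in protocol 4.3.3.
2. **Protocol 4.3.7 or the eCRF completion guideline.** Record such worsening as a new AE, dated at the worsening, with its own severity and causality assessment. Without that date the new SAP clause cannot be programmed reliably. Close the earlier record at the same date and keep it as a non-TEAE, so that the event is not counted twice as treatment-emergent.
3. **Causality rules.** Reconcile the 4.3.7 footnote with 4.3.3, so that the automatic unrelated label does not extend to worsening after exposure.
4. **Version check.** Confirm the wording against protocol Version 3.0 before editing.

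The cost is a clause in the SAP, a short protocol alignment and a line in the completion guideline. The downside is a slightly higher TEAE count.

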8 CONCOMITANT MEDICATION AND TREATMENT

8.1 Prior and Concomitant Medication

All medications as documented by the investigator will be coded using Anatomical Therapeutic Chemical (ATC) classification codes via the World Health Organization Drug Classification Dictionary (WHO-DD). All medications will be summarized and sorted alphabetically by medication class (ie, ATC level 2) and medication sub-class (ie, ATC level 4). If the ATC level 2 or 4 term is missing, the higher ATC level term will be used in the medication summary table and data listing.

Prior medications and concomitant medications will be summarized separately either overall (prior medications) or by study phase (concomitant medications). Prior medications are defined as any medication ended prior to the start of study treatment (ie, start of the infusion at Baseline/SC#1). Concomitant medications are defined as any medication started on or after the start of study treatment or any medication taken prior to the start of study treatment and continued after the start of study treatment during the study.

The following conservative imputation rules will be used for missing or partial end date/time information in order to determine whether a medication is prior or concomitant (ie, the unknown portions of a medication end date/time will be assumed to be as late as possible):

- Note: year is required on the eCRF, except for ongoing medication
- If the entire end year, date and time values are missing (ie, ongoing medication), then no imputation is performed and the medication will be assigned to the “concomitant” category
- If the month is missing, impute “December”
- If the day is missing, impute the last day of the month (ie, “28/29/30/31” depending on the year and month)
- If the hours are missing, impute “23”
- If the minutes are missing, impute “59”

The imputed medication end date/time will then be compared with the start of study treatment to determine if the medication is prior or concomitant.

Note the imputed end date/time will only be used to determine whether a medication is prior or concomitant. The start/end dates/times reported on the eCRFs will be presented in the listings.

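### The rule for incomplete AE start dates can count events that resolved before the first IGSC 20% infusion as treatment-emergent, because the late-filled onset is not checked against the resolution date

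*SAP*

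**What the plan says.** SAP 11.1 defines a TEAE by comparing AE onset with the moment the SC#1 infusion begins. For incomplete start dates it turns to "the same algorithm for missing or partial date information described in Section 8.1", and it limits that use to deciding the AE's treatment-emergent status.

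SAP 8.1 introduces that algorithm for medications: "The following conservative imputation rules will be used for missing or partial end date/time information". Its principle is that "the unknown portions of a medication end date/time will be assumed to be as late as possible". A missing month becomes December; for the day, "If the day is missing, impute the last day of the month"; a missing time becomes 23:59. If the whole end date is missing, the medication is taken as ongoing and classed as concomitant. A closing note restricts the filled date to the prior/concomitant decision and keeps the reported dates in the listings.

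Neither section compares a filled AE onset with the date the AE resolved. Protocol 4.3.7 requires that date for every AE.

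A separate sentence in SAP 11.1 covers study phase: "TEAEs will be further characterized within each study phase based on the onset date/time relative to the first infusion date/time" of each phase. It gives no rule for an incomplete onset.

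**The concern.** Filling late is natural for a medication end date: if the drug might still have been in use at SC#1, it is treated as concomitant. A start date differs because it has an upper limit, the date the event ended. The SAP borrows the end-date rule without adding that limit. The lack of adaptation shows in the branch for a wholly missing date, which means an ongoing medication and has no counterpart for an AE start.

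Pre-treatment AEs do occur in this design. They are collected from consent (Protocol 4.3.1), through a Screening/Previous Regimen Phase of up to 8 weeks (Protocol 3.6.1) in which subjects are infused with their earlier IgG product and infusion reactions are recorded (Protocol 3.6.2.1). At stake is whether some of these events, already over before any IGSC 20% was given, enter the TEAE incidence, the event totals and the rates per infusion and per exposure week.

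**Working it through.** The plan gives no figure on this point, so there is none to reproduce. The check applies the rule as written.

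**Inputs**
- Fill rule (SAP 8.1): month to December, day to last of month, hour to 23, minute to 59.
- S: start of the SC#1 infusion, the TEAE reference point (SAP 11.1).
- R: AE resolution date/time (collected, Protocol 4.3.7).
- Pre-treatment window: up to 8 weeks, 8 × 7 = 56 days (Protocol 3.6.1); 4 weeks, 4 × 7 = 28 days, for subjects entering on SCIG (Protocol 3.6.2.1).

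**Rule as written.** Let T be the latest date/time compatible with the known parts of the onset. The AE is a TEAE if T ≥ S. R does not enter.

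**Illustrative cases (dates assumed)**
1. Onset Mar 2016, R = 10 Mar, S = 20 Mar. T = 31 Mar 23:59, which is after S, so TEAE. The working onset is 31 − 10 = 21 days after resolution.
2. Onset 2017 only, R = 9 Mar 2017, S = 20 Mar 2017 10:00. T = 31 Dec 2017 23:59, so TEAE.
3. Onset 20 Mar 2017 with time missing, R = 09:00 that day, S = 10:00. T = 23:59, so TEAE.

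**Rule with a cap.** Use min(T, R) instead of T. The three working onsets become 10 Mar, 9 Mar and 09:00, all before S, so all three AEs are non-TEAE.

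In general, min(T, R) ≥ S needs both T ≥ S and R ≥ S. If R < S, the AE is never a TEAE. If R ≥ S, or the AE is ongoing, the answer is the same as under the present rule. The cap changes only the events that are wrong now.

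**How often, under stated assumptions.** Onset is taken as uniform over the pre-treatment window, Baseline as uniform over a 4-year calendar, and AE duration as 3, 7 or 14 days. The shares below are of AEs that have an incomplete start date and resolved before SC#1, and that the present rule would call TEAEs.

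| Window | Missing part | 3 days | 7 days | 14 days | With cap |
|---|---|---|---|---|---|
| 56 days | day | 22.5% | 17.7% | 10.0% | 0% |
| 28 days | day | 47.4% | 40.9% | 29.4% | 0% |
| 56 days | month and day | 91.8% | 91.2% | 90.3% | 0% |
| 28 days | month and day | 95.6% | 95.1% | 94.1% | 0% |

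These are shares of an unknown number. The documents do not say how many AEs will have incomplete start dates.

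**The case against.** **The rule errs on the safe side.** Late filling adds TEAEs and hides none. This stands, and it is why the late fill should be kept. It does not justify counting an event whose resolution date rules out treatment emergence.

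**Few events will be affected.** Onset and resolution date/time are required AE fields and AEs are elicited at each visit (Protocol 4.3.7); monitors check the eCRF against source (Protocol 6.2). An error needs an incomplete onset, a known end before SC#1, and known parts that still allow a later date. This also stands. In addition, Protocol 4.3.7 has AEs before exposure labelled unrelated, so if that is followed the over-count falls on all-cause TEAEs and not on suspected ADRs.

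**The impossible date may never be shown.** If the 8.1 note on listings carries over to AEs, onset after resolution exists only in a working variable. That is fair, but the wrong flag still reaches the summary tables.

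**A stronger reading is tempting: that the rule also moves Stage 1 events into Stage 2 and biases the by-stage rates.** The documents do not support it. SAP 11.1 confines the algorithm to the treatment-emergent decision, SAP 8.1 confines the filled date to its own classification, and phase assignment is a separate sentence that does not mention a filled date. What exists is a gap: phase depends on onset, and nothing says what to do when onset is incomplete. The shift would arise only if a programmer reused the filled date. In that case, with onset uniform over the 91 days of Stage 1, about 16% of Stage 1 AEs with the day missing and 87% with the month missing would land in Stage 2. That is a reason to rule out reuse, not a bias written into the plan.

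**Conclusion.** The point holds for the TEAE flag. As written, SAP 11.1 can class an AE known to have resolved before the SC#1 infusion as treatment-emergent, which contradicts the definition in the same section. The result is an over-count of TEAEs and of the rates built on them. Among day-missing AEs that resolved before SC#1, the share misclassified is about 10% to 23% for a 56-day window and 29% to 47% for a 28-day window, given uniform dates and durations of 3 to 14 days. The absolute number is unknown and probably small. Nothing in the documents shows the primary SBI test depending on this rule, and they do not mandate a shift of events between stages. It is worth correcting before database lock because the remedy is exact and uses data already collected.

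**What to change.** In SAP 11.1, replace the bare cross-reference with a short start-date rule:

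- Fill unknown parts of an AE onset as late as possible, but never later than the AE resolution date/time. If the resolution date is itself incomplete, fill it late too, so that the cap acts only when resolution before SC#1 is certain.
- Class any AE that resolved before the start of the SC#1 infusion as non-TEAE.
- State that the filled onset is used only for the TEAE flag, not to assign study phase or to decide whether an AE falls in the 72-hour temporal-association window. Say separately how TEAEs with incomplete onset are handled in by-phase tables.

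Setting an incomplete onset to the first infusion date is a common alternative but is not preferable here. For AEs not resolved before SC#1 it gives the same TEAE flag and, if carried forward, it would push partial-date events into Stage 1 and the 72-hour window.

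The cost is one SAP paragraph, a small programming change and slightly fewer TEAEs. No new data are needed.

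### SAP 11.1 confines the by-week and overall local-reaction table to non-AE reactions, so no specified table gives the unduplicated percentage of subjects with any local infusion site reaction

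*SAP*

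**What the plan says.** Protocol 4.3.1 requires every local infusion site reaction to be recorded in the eCRF. It treats as AEs the subset that interrupted or stopped an infusion, needed medication, or affected the subject's general condition in the investigator's judgment. SAP 3.2 keeps this structure.

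SAP 11.1 then reports the two groups separately:

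- **AE-qualifying reactions.** Those "that meet the definition of an AE (see Section 4.3.1 of the protocol for details) will be summarized with other AEs". The AE tables are organised by SOC and preferred term and "will be summarized by study phase using descriptive statistics". Their counting rule is that "a subject will only be counted once per system organ class or preferred term". Event totals and rates are also given: "Summaries will also be provided for the total number of events, the rate per infusion, and the rate per exposure week". A further output covers AEs close to an infusion: "Temporally-associated AEs defined as those occurring during or within 72 hours following the end of investigational product infusion will be separately summarized".
- **Non-AE reactions.** "Local infusion site reactions during the IGSC 20% treatment phase that do not meet the definition of an AE will be separately summarized", by infusion week and overall, with subject numbers and percentages, event totals and the rate per infusion. The listings are split in the same way: "Local infusion site reactions that do not meet the definition of an AE will be listed separately".
- **Plot.** "The percentage of subjects with any local infusion site reactions and the rate per infusion will also be plotted", against infusion week. This sentence does not carry the non-AE qualifier.

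Protocol 5.1.5 says that local infusion site reactions will be summarised in the same manner as AEs (events, and number and percentage of subjects). It adds that they will be tabulated for the whole study and by infusion week. The synopsis repeats the tabulation. Neither place limits it to non-AE reactions.

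**The concern.** Tolerability is a stated safety objective, and for a weekly subcutaneous product a reader will want to know what percentage of subjects had any local reaction. The SAP's only whole-treatment subject percentage for local reactions as a group leaves out the AE-qualifying ones. By the protocol's own definition these are the more consequential: they interrupted or stopped an infusion, needed medication, or affected the subject's general condition.

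The separate outputs do not fill the gap. A subject may have a non-AE reaction one week and an AE-qualifying reaction another, so the subject percentages cannot be added. The combined figure would have to be rebuilt from two listings. A reader could also take the dedicated table's percentage to describe all local reactions.

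**Working it through.** The plan states no figure on this point, so there is nothing to reproduce. The check compares the texts and then bounds the missing percentage.

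**Step 1: which output could give the number?**

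| SAP 11.1 output | Reactions covered | Each subject counted once for any local reaction? | By infusion week? |
|---|---|---|---|
| AE tables | AE-qualifying | No: once per SOC or preferred term, no grouped local-reaction row specified | No: by study phase |
| 72-hour summary | AEs only | No | Not specified |
| Dedicated table | Non-AE only | Yes, but for the non-AE set only | Yes |
| Plot | Unclear | No: a weekly percentage, not a whole-treatment one | Yes |
| Listings | Both, in separate listings | Not a summary | Not a summary |

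No row gives the whole-treatment percentage for AE and non-AE reactions combined.

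**Step 2: events and subjects behave differently.** A reaction either meets the AE definition or does not, so the two event sets are disjoint. Total events and the rate per infusion can be obtained by adding the two sources, provided the local-reaction terms can be identified in the AE tables. Subjects can be in both sets, so their percentages cannot be added.

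**Step 3: bounds.** Let a be the number of subjects with a non-AE reaction, b the number with an AE-qualifying reaction, and N = 60 (planned enrolment, SAP 4.3). The number with any reaction is:

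- full overlap: max(a, b)
- independence: N × [1 − (1 − a/N)(1 − b/N)]
- no overlap: min(N, a + b)

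All values of a and b below are assumed.

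| a, b | Full overlap | Independence | No overlap | Dedicated table shows |
|---|---|---|---|---|
| 30, 6 | 30 (50%) | 60 × (1 − 0.5 × 0.9) = 33 (55%) | 36 (60%) | 50% |
| 30, 12 | 30 (50%) | 60 × (1 − 0.5 × 0.8) = 36 (60%) | 42 (70%) | 50% |
| 18, 18 | 18 (30%) | 60 × (1 − 0.7 × 0.7) = 30.6 (51%) | 36 (60%) | 30% |

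No overlap is an arithmetic limit, not an expectation over up to 52 weekly infusions. If subjects with AE-qualifying reactions also tend to have non-AE ones, the value lies between the first two columns.

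**Step 4: b itself may not be readable.** Suppose three local-reaction preferred terms in the AE table show 6, 4 and 2 subjects (assumed). Then b can be anything from 6 (the smaller groups lie within the largest) to 6 + 4 + 2 = 12 (no subject is in two rows).

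**The case against.** The case for leaving the SAP as it is has several parts.

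- **Nothing is lost.** A reader might infer that the SAP drops the more serious local reactions. It does not. They are in the AE tables (SOC and preferred term, severity, causality, rate per infusion), the 72-hour summary and the listings, and SAP 8.2.1 summarises infusion interruptions. This stands. Nor is the overall event rate necessarily understated, since the two event sets can be added.
- **The SAP may match its own protocol version.** A reader might infer that the SAP contradicts its governing protocol. That cannot be shown: SAP 1 cites Version 3.0 of 21 Mar 2017, while the supplied protocol's amendment summary ends at Version 2.0 of 22 Jul 2016. The comparison holds for the supplied text only. The gap inside the SAP does not depend on it.
- **The supplied protocol never asks in words for AE and non-AE reactions in one table.** True, and separate reporting follows its subset definition. But it calls that group a subset of local infusion site reactions, so the unqualified term in section 5.1.5 most naturally means the whole set.
- **The plot may already cover all reactions by week.** On its plain words it may. The by-week gap is then a figure in place of a table. If the plot follows the restricted table instead, its wording is loose. Either way it cannot supply the whole-treatment percentage.
- **The figure could be produced later.** SAP 1 allows unplanned analyses documented in the CSR. That is weaker than specifying the output now.

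**Conclusion.** The point holds as a minor reporting correction. SAP 11.1 restricts a tabulation that the supplied protocol plans without restriction, and no specified table gives the unduplicated percentage of subjects with any local infusion site reaction over the treatment phase. The dedicated table's percentage is a lower bound for it. By-week reporting of all reactions rests on a plot whose scope is ambiguous.

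The size cannot be estimated from the documents. The bounds show that the combined percentage cannot be identified from the separate tables. They do not show that the difference is large. A reader might infer that the combined figure must be less favourable, but with full overlap it equals the non-AE figure, so it may be the same or higher. The study is single-arm, this output is descriptive, and the primary SBI analysis is unaffected.

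**What to change.** In SAP 11.1, specify the by-week and overall table for all local infusion site reactions, AE and non-AE combined, counting each subject once within each week and once overall. Give the number and percentage of subjects, the number of events and the rate per infusion, with AE and non-AE sub-rows. State that the plot uses the same all-reaction set.

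The cost is a few table rows and one clause. No new data are needed, because all local reactions are already recorded in the eCRF. The AE tables, the 72-hour summary and the listings can stay as they are.
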